#### Outcomes

Primary outcome: Systolic blood pressure (SBP) in mm Hg. Blood pressure readings will be extracted from the electronic healthcare record and from the Hypertension Plus system. Readings will be identified as having been taken by a healthcare professional in the clinic or by the patient at home. Readings derived from 24-hour ambulatory BP monitoring will be excluded. Values outside the range 70-250 mm Hg will be excluded. Where multiple readings are recorded on a single day, the lowest value will be selected.

Secondary outcomes:

- Diastolic blood pressure (DBP) in mm Hg, extracted from the electronic healthcare record or the Hypertension Plus system in the same manner as SBP readings. Values outside the range 40-150 mm Hg will be excluded.
- Blood pressure control (binary variable) defined using SBP and DBP readings. Controlled BP will be defined as SBP <140 mm Hg and DBP <90 mm Hg for clinic readings or SBP <135 mm Hg and DBP<85 mm Hg for home readings. Uncontrolled BP will be defined as the presence of any clinic or home SBP or DBP reading above these thresholds.
- Primary care workload defined as the number of face-to-face and telephone consultations where hypertension or hypertension monitoring was listed as the primary problem. Sensitivity analyses will assess whether the addition of BP readings or antihypertensive treatment records to the definition of workload affects these results

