## Statistical modelling

Multilevel models and Difference-in-Differences (DiD) analysis will be used to describe changes in outcomes over time (12 months before and after "Time 0") and the effect of the introduction of the Hypertension Plus system. Difference-in-differences (DiD) allows comparison of differences in outcomes, TM101-A

Protocol Template for a Research Study\_version 15.0 CONFIDENTIAL
© Copyright: The University of Oxford and Oxford University Hospitals NHS Foundation Trust 2019 Page 18 of
28

before and after an intervention, between groups. Bias from unobserved fixed variables within each group is automatically accounted for in this type of analysis but bias from variables that affect allocation to the exposed an unexposed group must still be accounted for.

• Primary outcome (SBP) and secondary DBP outcome:

For the primary outcome (SBP) and secondary outcome of DBP, multilevel linear models will be used to model these outcomes over time, including a fixed linear effect for time relative to "Time 0" and random effects for patient and practice level average BP. The models will also include as fixed effects, an indicator for whether each BP was measured in the clinic or at home, an indicator for exposure and, to estimate difference-in-differences, interaction terms between the exposure and time period variable (initial model).

The addition of random effects for patient and practice level trends into the initial model will be considered by comparing models via the likelihood ratio test and Akaike Information Criterion (AIC), with terms retained if model fit is significant improved or the AIC is lower. Covariates will be included as fixed effects without selection once the initial model is finalised. To account for autocorrelation between BP measurements in the same individual, standard errors will be estimated using robust methods and more specifically the Huber-White Sandwich estimator of the variance which can adjust for within-cluster correlation.

The effect of the Hypertension Plus intervention at 6 and 12 months will be estimated by comparing the estimated BP values in the exposed at unexposed groups at these time points, as derived from the models. These estimates, and estimates from the models will be summarised in tables including p-values and 95% confidence intervals.

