## Subgroup analysis

Analyses and modelling above will be repeated in the following subgroups:

• Men and women

TM101-A

Protocol Template for a Research Study\_version 15.0CONFIDENTIAL© Copyright: The University of Oxford and Oxford University Hospitals NHS Foundation Trust 2019Page 19 of28

- Age >65 years; >80 years
- Mean SBP before "Time 0" (>160 mm Hg)
- Previous history of myocardial infarction or stroke
- By CCG area
- Users of the system for at least 6months defined as coded data identifying use recorded in the clinical record at both baseline and between months 6-12
- People with baseline blood pressure ≤140/90 compared to those >140/90mmHg
- Deprivation score (High vs Low)
- Ethnicity

Sample size requirements for this study were determined through simulation, as there is little statistical literature for sample size requirements for multilevel modelling. Data was simulated for systolic BP measurements, nested within patients, nested within practices, with the same structure as that detailed in the statistical modelling section. Normal distributions for BP values and variances around patient and practice mean values were assumed (reflecting random intercept terms). A global mean BP of 148 mm Hg was assumed, with practice variation (standard deviation, SD) of 5 mm Hg about this mean. Within a practice, patient variation (SD) was assumed as 17 mm Hg and measurements within a patient were assumed to vary by 10 mm Hg (SD) about the patient mean. The effect of time was assumed to be 0, clinic BP measurements were assumed to be 5 mm Hg higher than home measurements and 25% of patients were expected to take up the Hypertension Plus system.

Assuming an effect size of -3 mm Hg (BP 3 mm Hg lower in patients using the Hypertension Plus system) and a minimum of 4 BP measurements for each patient, 1000 simulated datasets were created and multilevel models as described in the statistical modelling section were fitted to each simulation. This demonstrated that to achieve 90% power at the 5% significance level for the effect of the Hypertension Plus system, 100 patients each drawn from 8 general practices would be required for this study (800 patients in total, 91% power).

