When assuming a smaller effect size (-1 mm Hg) or greater variation (practice SD=10 mm Hg, patient SD = 22 mm Hg or measurement SD = 14 mm Hg), the required sample size was 200 patients from 35 practices, 100 patients from 8 practices, 100 patients from 8 practices or 100 patients from 14 practices respectively. Combining all of these conservative assumptions led to a required sample size 300 patients drawn from 42 practices (12600 patients in total, 90% power).

Assuming an average practice size of 8000 people, a 14% prevalence of hypertension, and an uncontrolled hypertension prevalence of 30%, we expect 336 eligible patients per practice. Considering the scenarios above, that study power is more greatly influenced by the number of practices rather than the number of patients, and the possibility of withdrawal of up to 10% of practices. We anticipate that at least forty and up to approximately sixty practices will contribute, hence adequate power for the comparisons should be available.

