# TM101-A

Protocol Template for a Research Study\_version 15.0

© Copyright: The University of Oxford and Oxford University Hospitals NHS Foundation Trust 2019 Page 21 of 28

		intervention/control in the analysis b) BP control rather than BP level in analyses
(3) High variability in the frequency of readings	Home readings can be several times per day or week whereas clinic readings tending to be 1-4x per year. Furthermore, attendance at clinic may be for some other reason meaning those who attend or not are different systematically	
 
a) Primary analysis utilises all available data
 
b) Consider sensitivity analysis using standardisation of readings over time. This means that we take bp values at fixed time points more specifically at 6 and 12 months with value closest to that time point being the one used for the analysis.
 

(4) Contamination of readings	Home readings can be coded as clinic readings. The automated importing of Hypertension Plus readings into the clinical record should avoid this but it is possible that home readings in the comparator group may also be contaminated as may be readings prior to the implementation period.	
 
a) This may be a problem in both groups
 
b) Hypertension Plus readings will be labelled as such
 

(5) Regression to the mean	People chosen on the basis of raised baseline readings are more likely to have subsequently controlled BP	Both intervention and comparison groups will be chosen using same attributes Consideration of need for matching.
(6) Measurement error	Both operator, system and monitor errors are possible	Operator errors may be more likely by patients but evidence of operator bias is more likely for clinicians. Most of these errors will be similar in both groups
(7) End digit preference	People tend to be more likely to record readings ending in zero	
 
a. We will investigate prevalence in both intervention and comparator groups
 
b. Adjusting for the control/intervention group in a mixed model should be
 

		able to take into account for potential differences in the magnitude of digit preference
(8) Withdrawal bias	Patients may not use the Hypertension Plus system consistently.	We will use intention to treat approach so individuals with any Hypertension Plus activity recorded will be assigned to intervention.

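### Keeping only the lowest same-day blood pressure can create a false benefit when users' home days hold more readings than other home days, and the clinic/home indicator does not fully remove it

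*Protocol*

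**What the plan says.** Section 11.2 (Outcomes) defines SBP from readings in the health record and in the Hypertension Plus system, each labelled clinic or home, and then fixes the daily selection: "Where multiple readings are recorded on a single day, the lowest value will be selected". DBP is "extracted from the electronic healthcare record or the Hypertension Plus system in the same manner as SBP readings", so the rule carries over. It is worded identically for users and non-users, for both periods and for both settings.

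On how often readings occur, row 3 of the table in section 12.3 says: "Home readings can be several times per day or week whereas clinic readings tending to be 1-4x per year". Row 4 of the same table accepts that home readings may be coded as clinic readings, and that this may affect the comparator group and the time before implementation.

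The primary model (section 11.2, Statistical modelling) contains "an indicator for whether each BP was measured in the clinic or at home" as one fixed effect. It estimates the effect of the system through the interaction of exposure with period. The sample size text plans for two effects: "Assuming an effect size of -3 mm Hg", and "When assuming a smaller effect size (-1 mm Hg) or greater variation" in the conservative scenarios.

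**The concern.** The minimum of several readings is a biased summary of a day's pressure, and the bias grows with the number of readings. A rule that is the same for everyone therefore has unequal effects when the number of readings per day is unequal. Uploading app readings begins at Time 0 and only in users. That is the same contrast that the exposure-by-period term measures, so a change in how many readings a day holds could be read as a change in blood pressure.

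The primary outcome and DBP are both at stake. A system with no effect could appear to lower pressure. Recruiting more practices would not help, because it shrinks the standard error and leaves the bias unchanged. None of the eight rows in section 12.3 names the selection rule as a source of bias. The sensitivity analysis in row 3 (value nearest 6 and 12 months) is only to be considered, and nothing says that it would bypass the daily selection.

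**Working it through.** **Inputs from the protocol (section 11.2, sample size text).** Practice SD 5, patient SD 17 and measurement SD 10 mm Hg ("measurements within a patient were assumed to vary by 10 mm Hg (SD) about the patient mean"); 25% uptake; at least 4 readings per patient; effect -3 mm Hg; 8 practices of 100 patients; 5% level, taken here as two-sided. Stated power: 91%.

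**Not given, so assumed.** Same-day SD: 5 to 10 mm Hg, where 10 is the base-case total within-patient SD and so an upper value for that case. Readings per home day: 2 or 3. Share of readings taken at home: three cases below. Timing of the 4 readings around Time 0.

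**Step 1: reproduce the stated power.** In a within-patient change, the patient and practice terms cancel. With b readings before and a after, the variance of the change is 10² × (1/b + 1/a). With 200 users and 600 non-users, SE = √[variance × (1/200 + 1/600)].
- 2 before, 2 after: variance 100, SE 0.816, power Φ(3/0.816 - 1.96) = 95.7%.
- 1 before, 3 after: variance 133.3, SE 0.943, power 88.9%.
- Full multilevel model by generalised least squares, readings spread at random over -12 to +12 months, half of them home: SE 0.933, power 89.5%.

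The 91% is reproduced to within 2 points under the last timing assumption, so the model used below is a fair stand-in for the planned one.

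**Step 2: shift from taking the minimum.** For k independent normal readings, the expected minimum lies 0.564 (k = 2), 0.846 (k = 3) or 1.029 (k = 4) SDs below the mean, and 0 below it for k = 1. Multiplying by the same-day SD:

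| Same-day SD | k = 2 | k = 3 |
|---|---|---|
| 5 | -2.8 | -4.2 |
| 7 | -3.9 | -5.9 |
| 10 | -5.6 | -8.5 |

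**Step 3: what remains in the exposure-by-period term.** The shift S was projected through the model, which included time, period, exposure, the clinic/home indicator and exposure × period. The true effect was zero.

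(a) *All home days hold the same k.* Every home reading moves by S, the home coefficient absorbs it, and the bias is 0.0 in every case.

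(b) *Users' home days after Time 0 hold k readings; all other home days hold one.* Columns give the home share of users' readings after Time 0 / the home share of all other readings. Bias in mm Hg:

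| k | Same-day SD | 50% / 10% | 80% / 10% | 90% / 25% |
|---|---|---|---|---|
| 2 | 5 | -1.1 | -1.8 | -2.4 |
| 2 | 7 | -1.6 | -2.6 | -3.4 |
| 2 | 10 | -2.2 | -3.6 | -4.9 |
| 3 | 5 | -1.7 | -2.8 | -3.6 |
| 3 | 7 | -2.3 | -3.9 | -5.1 |
| 3 | 10 | -3.2 | -5.5 | -7.2 |

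For example, at k = 2 and SD 5 the carried fraction of S is 1.09/2.82 = 39%, 1.83/2.82 = 65% and 2.44/2.82 = 87% across the three columns.

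A separate simulation took 4000 patients, 25% users, 12 home days per user, 0 to 2 clinic readings per user after Time 0, a 5 to 30% home share elsewhere and a same-day SD of 5 to 7. It gave -0.9 to -4.2 mm Hg for 2 readings a day. Using the day's mean instead, the estimate was zero within simulation noise.

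**Step 4: consequence for the test.** With SE 0.933 and no true effect, a bias of 1, 2 or 3 mm Hg gives a significant result with probability 19%, 57% or 90%. In the combined conservative scenario (12,600 patients, stated power 90% for -1 mm Hg), a bias of 1 mm Hg would be declared significant about 90% of the time by the protocol's own figure.

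**The case against.** The strongest reply is that the model already has a clinic/home term, and that the rule treats everyone alike. Both statements are correct. A reader might infer that lower home minima set against single clinic readings are enough to create the bias. They are not: step 3(a) shows that a shift common to all home readings disappears entirely. A reader might also infer that the rule operates only in users once they have started. It does not: section 11.2 applies it to all readings, and only the number of readings per day can differ.

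The reply goes further. The remark in section 12.3 about several readings per day concerns home readings in general, not app readings alone. The clinic figure is a yearly frequency and does not say that a visit yields one reading; repeated clinic readings would be minimised too, which narrows the gap. Row 4 acknowledges home readings in the comparator group and before implementation. Nothing shows that those days are single entries.

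All of this stands, and it makes the size conditional. It does not make the rule safe. Zero bias needs equal numbers of readings per home day across groups and periods, and the protocol neither claims nor arranges that. The miscoding expected in row 4 further weakens the indicator, although its contribution was not quantified here. Sections 11.1 and 12.4 allow a later analysis plan to add detail, but the rule as written would stand until someone changed it.

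**Conclusion.** The rule can bias the primary SBP estimate, and DBP by the same mechanism, toward benefit, and the single clinic/home indicator does not guarantee its removal. For SBP, with a same-day SD of 5 to 10 mm Hg, the bias runs from 0 to about -5 mm Hg for 2 readings a day and to about -7 mm Hg for 3. The zero end applies when home days hold equally many readings everywhere. The non-zero values, from about -1 (2 a day) or -2 (3 a day), apply when home readings outside the users' post-start period are single entries.

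It is tempting to say that the rule creates a false benefit about as large as the assumed effect. The protocol does not support that: readings per day, same-day SD and home share are all unstated. In these calculations the bias reaches roughly -3 mm Hg mainly when most of the users' later readings are home readings and other home days hold one reading. The direction is secure wherever users' home days hold more readings than other home days; the size is not known. Because even 1 mm Hg equals the whole conservative effect, the rule should be changed before analysis.

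**What to change.** Replace the selection rule for SBP and DBP with: *Where multiple readings of the same type (clinic or home) are recorded on one day, their mean is used, in both groups and both periods.* Keep the lowest-value rule as a sensitivity analysis only. The expected selection shift is then zero for any number of readings.

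The cost is one sentence, with no new data, since the readings are already extracted. There are two downsides. The estimated benefit may come out smaller. Day means also vary in precision with the number of readings behind them; the robust standard errors already planned allow for this.

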## 2. LAY SUMMARY

Hypertension Plus was developed to help patients measure their blood pressure (BP), send the results to the GP, and communicate about changes they could make to their treatment. Hypertension Plus reminds patients to measure their BP, and reminds patients and their GPs and other clinical staff when they need to take action.

The NIHR Applied Research Collaboration (Oxford and Thames Valley) is funding "A service evaluation of the implementation of Hypertension Plus" know as the "SHIP" study for short. The SHIP study will

explore how well Hypertension Plus works in GP surgeries, in particular how many patients choose to use it, how well their blood pressure is controlled, and what impact it has on the workload of GP practices.we will look at the impact on the cost of care, and how many prescriptions are issued.

The SHIP study will use anonymised routinely collected data, recorded by practices and patients in their routine care. We will compare data from patients who have chosen to useHypertension Plus with those who haven't. For those patients who use Hypertension Plus, we will compare results from before and after they start to use it. There is no way of the research team knowing who the patients are.

Summaries of the results will be shared with GP practices, patients and commissioners of care. The research team will publish the results in journals and present at conferences and share them in traditional and social media.

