# 3. SYNOPSIS

Study Title	A Service evaluation of the Hypertension-Plus Implementation – implementing a hypertension self-monitoring/management service in primary care				
Internal ref. no. / short title	The SHIP study				
Study registration	tbc				
Sponsor	University of Oxford Joint Research Office [name]				
Funder	NIHR ARC Oxford and Thames Valley [name] [name] [name] [contact] Email: arc. [contact]				
Study Design	Observational Service	e Evaluation			
Study Sites	GP practices				
Study Participants	Adult patients (>18y) with hypertension				
Sample Size	Anonymised records	from approximately 60 practices			
Planned Study Period	From January 2022 fo following recruitment	er around 12 months with follow-up t.	o for 12 months		
	Research Questions	Outcome Measures	Timepoint(s)		
Primary	Does Hypertension Plus lead to lower systolic blood pressure?Systolic blood pressure of system us compared to before and o patients		Over the first year of system use compared to year before and control patients		
Secondary	Will people with hypertension use the HypertensionProportion of hypertension register signing up for Hypertension Plus in first 6 months of implementation in each practice.Over the first ye of system use				
	Does Hypertension Plus lead to lower diastolic blood pressure?Diastolic blood pressureOver the first year of system use compared to year before				

	Does Hypertension Plus lead to better control of blood pressure?	Proportion controlled below target	Over the first year of system use compared to year before
	Does Hypertension Plus reduce practice workload?	Consultation rate recorded in clinic record before and after use of Hypertension Plus system	Over the first year of system use compared to year before
Intervention	Hypertension Plus system		
Comparator	We will use both interrupted case series (before/after) and difference of differences approaches meaning that the comparator is usual care without the use of Hypertension Plus. Practices that implement the system later will be used to as a further level of comparator.		

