## 7.1 The Hypertension Plus System

Hypertension Plus is a primary care remote hypertension management and medication titration platform. Based on workflow algorithms proven in randomised controlled trials through the TASMIN studies, and decision-support tools compliant with NICE guidelines. Hypertension Plus is intended to facilitate remote population health management, improving outcomes and increasing efficiency of hypertension management in primary care.

The system combines a web based dashboard for professionals, which both reads and writes data to the practice clinical system, with a mobile phone "app" which is downloaded by participating patients and used to upload blood pressure and other information.

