## 9.5. Description of study intervention and comparator

## 9.5.1. Description of study intervention

The study intervention is "Hypertension Plus". People using the system will use an app to send blood pressure readings securely to a central dashboard. Data will be recorded automatically in the clinical record via appropriate SNOMED codes allowing identification of active users. An active user will be someone with a record of having used the Hypertension Plus system in their clinical record with the appropriate SNOMED code. This definition will be regardless of how much use is made of the system and once labelled as having received the intervention, patients will be analysed in that group on an "intention to treat basis".

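### The workload outcome counts only face-to-face and telephone consultations, so hypertension work moved to remote modes is missed and the rate ratio is biased toward a saving

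*Protocol*

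**What the plan says.** One secondary question in the Synopsis (section 3) and in the objectives table is whether the system reduces practice workload. The measure named there is "Consultation rate recorded in clinic record before and after use of Hypertension Plus system", with no restriction on the type of contact. Section 11.2 (Outcomes) narrows it: "Primary care workload defined as the number of face-to-face and telephone consultations where hypertension or hypertension monitoring was listed as the primary problem". The next sentence adds a check: "Sensitivity analyses will assess whether the addition of BP readings or antihypertensive treatment records to the definition of workload affects these results".

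The intervention itself is described in remote terms. Section 7.1 states: "Hypertension Plus is a primary care remote hypertension management and medication titration platform". It continues: "The system combines a web based dashboard for professionals, which both reads and writes data to the practice clinical system". The Lay Summary (section 2) says that patients send results to the GP and communicate about treatment changes, and that the system "reminds patients and their GPs and other clinical staff when they need to take action". On users' readings, section 9.5.1 says: "Data will be recorded automatically in the clinical record via appropriate SNOMED codes allowing identification of active users".

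The workload model in section 11.2 (Statistical modelling) is a negative binomial on consultation totals before and after Time 0, with an exposure-by-period interaction. Section 12.5 costs the consultation time recorded for setting up and delivering the service, and estimates time not recorded in the clinical system. Both feed the cost analysis.

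**The concern.** The outcome is defined by two contact modes, while the intervention gives staff another way to do the same job. Reviewing readings on a dashboard, acting on a prompt or sending a message is practice work, but it is neither face-to-face nor telephone. The protocol does not add such work to the workload outcome, and it does not say that such work is coded as a consultation.

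Any work that changes mode because of the system does so in users after Time 0. Difference-in-differences removes fixed differences between groups. It does not remove a change in what the outcome can see that starts with exposure. The uncounted work would therefore be read as an effect of the system. Hypertension Plus is a paid-for service and the results go to commissioners of care, so a reported fall in workload that is partly a change of mode could mislead the people who decide whether to buy it.

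**Working it through.** **No figure to reproduce.** The protocol gives no baseline rate, effect size or power for workload. Its sample sizes (800 and 12600 patients) were simulated for systolic BP and serve below only as illustrative totals.

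**Size of the bias.** Let total hypertension contacts be unchanged, so the true rate ratio is 1.00. Let a share f of users' contacts after Time 0 move to uncounted modes. Then the counted ratio = 1 − f.

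| f (assumed) | counted ratio | true ratio |
|---|---|---|
| 10% | 0.90 | 1.00 |
| 20% | 0.80 | 1.00 |
| 30% | 0.70 | 1.00 |

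Here f is net of any similar shift in non-users. If users shift by u and non-users by c, the counted ratio is (1 − u)/(1 − c). With u = 30% and c = 10% it is 0.70/0.90 = 0.78, a net f of 22%.

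**Could such a bias reach significance?** Inputs from the protocol: 25% uptake (sample size text, section 11.2) and a 5% level (section 12.1), taken as two-sided. Assumed: 1 to 4 counted consultations per patient per year, and an overdispersion factor φ of 1 to 2. The approximate standard error of the log ratio is s = √[φ(2/(n_e·rate) + 2/(n_c·rate))], where n_e and n_c are the numbers of users and non-users. The chance of declaring a reduction is Φ(−ln(1 − f)/s − 1.96).

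Worked case: N = 12600, so n_e = 3150 and n_c = 9450; rate 1, φ = 2, f = 10%.
- s = √[2(2/3150 + 2/9450)] = 0.0411
- −ln 0.90 = 0.1054, and 0.1054/0.0411 = 2.56
- Φ(2.56 − 1.96) = Φ(0.60) = 73%

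| N | f = 10% | f = 20% |
|---|---|---|
| 800 | 9% to 45% | 28% to 97% |
| 12600 | 73% to nearly 100% | about 100% |

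Ranges cover rates 1 to 4 and φ 1 to 2.

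**What the sensitivity analyses would add.** Treatment records capture remote work that ends in a prescribing record. A dashboard review or message that changes nothing leaves none. BP readings are a different matter. Section 12.3 (row 3) says home readings can come several times per day or week, while clinic readings tend to come 1 to 4 times per year. If a user uploads weekly (an assumption) and every upload is counted, 52 records a year are added, against 1 to 4 for a non-user with clinic readings only. None of those 52 need involve staff.

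**Why dashboard actions should not simply be added in.** If each displaced contact generates m actions, the all-mode ratio is 1 − f + f·m. With m = 2 and f = 10%, 20% and 30% this gives 1.10, 1.20 and 1.30. These are counts of actions, not staff time.

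**The case against.** The strongest reply is that the shift is not documented. The protocol nowhere says that the system replaces consultations with dashboard work. It does not say by what mode patients and GPs communicate about changes. The dashboard writes to the clinical system, and section 12.5 expects some service-delivery work to be recorded as consultation time. If practices log that work as telephone contacts, it is counted. This stands: the direction of the bias is clear, but its size is unknown.

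A reader might also infer that only users are affected. The documents do not support that. Section 12.3 (row 4) expects home readings in the comparator group and before implementation, so some work outside the two modes may exist there too. The bias is the net difference in shift.

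A reader might say that the sensitivity analyses as a whole are biased toward a large increase, or that remote work vanishes from the study. Neither holds. The treatment-record version sees part of the remote work, and section 12.5 recognises unrecorded time. Section 12.3 says Hypertension Plus readings will be labelled, so they can be separated, and section 11.2 does not say that automatic imports will be counted as work. It does not exclude them either. Section 12.5 feeds costs and leaves the workload count unchanged.

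Finally, to say that the workload question cannot be answered at all is too strong. The face-to-face and telephone consultation rate is a legitimate quantity and can be estimated. It does not by itself support a conclusion on workload.

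**Conclusion.** The point holds for the main workload outcome. Work that users' practices move to dashboard, message or online modes after Time 0 is uncounted unless coded as a telephone consultation, and the interaction term is then biased toward a saving. The counted ratio is 1 − f when total contacts are unchanged: 0.90 to 0.70 for an assumed net shift of 10% to 30%. Neither f nor the consultation rate is in the documents, so these figures show how the bias scales and do not estimate it. Of the two sensitivity analyses, one captures remote work only in part and the other could overstate it. The primary systolic BP result is untouched. This should be settled before the data are drawn, because the contact codes must be in the extraction.

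**What to change.** - Define workload as all hypertension-related staff contacts of any mode coded in the record: face-to-face, telephone, video, and text or online. Report the face-to-face and telephone count as a component.
- Check whether the Hypertension Plus download planned in section 13 holds clinician dashboard actions. The protocol does not say. If it does, report them as a separate component and do not add them one for one, since an action is not equivalent to a consultation.
- In the BP-reading sensitivity analysis, exclude automatically imported Hypertension Plus readings, using the label promised in section 12.3.
- State that a fall in face-to-face and telephone consultations alone will not be reported as reduced workload.

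The cost is a few more codes in the extraction. A measured saving may turn out smaller.
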